4.2. Treatment Groups

Study sites will be allocated to either SoC group or the DSS group. Both groups will be following routine clinical care including local/national prescribing guidelines during the course of the study.

For those sites randomised to the DSS, there will be no patient intervention, but those sites will be trained on a DSS tool. The DSS is available in a web application that can be accessed on the Internet using the most common Web browsers, namely Google Chrome, Safari, Internet Explorer, Microsoft Edge, or Mozilla Firefox intended for clinicians to estimate the clinical benefit of any LLT regimen, whether monotherapy or combination therapies. The DSS does not recommend treatments but shows the expected ASCVD risk, absolute and relative ASCVD risk reductions and number needed to treat for the various treatments selected by the clinical user on the potential value of initiation of an add-on therapy for reducing the risk of recurrent cardiovascular (CV) events. Implementing the patient-specific recommendation remains at the clinicians' discretion. The DSS will be protected from unwanted use by asking its users to enter their OpenClinica credentials.

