5.4. Safety Variables

This trial is using the DSS system that is classified as a device. Therefore we will provide safety reporting on the following for the DSS arm only:

1. Adverse Device Effects (ADE): Any untoward and unintended response to a medical device.
 - This definition includes any event resulting from insufficiencies or inadequacies in the instructions for use or the deployment of the device.
2. Serious Adverse Device Effects (SADE): Adverse device effect that has resulted in any of the consequences characteristic of a serious adverse event or that might have led to any of these consequences if suitable action had not been taken or intervention had not been made or if circumstances had been less opportune.
 - Unanticipated Serious Adverse Device Effect (USADE): Any serious adverse device effect which, by its nature, incidence, severity or outcome, has not been identified in the anticipated AE's
 - Anticipated Serious Adverse Device Effects (ASADE): is an effect which by its nature, incidence, severity or outcome has been identified in the anticipated AE's. No ASADEs have been identified in this case.

Imperial Clinical Trials Unit	ZODIAC STATISTICAL ANALYSIS PLAN – MAIN ANALYSIS	V1 17 th Jan 2024
-------------------------------	--	------------------------------

The assignment of causality and severity for adverse device effects should be made by the investigator responsible for the care of the patient using the definitions in the tables below (**Error! Reference source not found.** and **Error! Reference source not found.**).

Table 3: Causality definitions of adverse device effects

Causality	Definition
Unrelated	No evidence of any causal relationship
Unlikely	There is little evidence to suggest there is a causal relationship (e.g. the effect did not occur within a reasonable time after use of the device . There is another reasonable explanation for the effect(e.g. the patient's clinical condition, other concomitant treatment).
Possible	There is some evidence to suggest a causal relationship (e.g. because the effect occurs within a reasonable time after use of the device). However, the influence of other factors may have contributed to the effect (e.g. the patient's clinical condition, other concomitant treatments).
Probable	There is evidence to suggest a causal relationship and the influence of other factors is unlikely.

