Definite	There is clear evidence to suggest a causal relationship and other possible contributing factors can be ruled out

Table 4: Severity definitions of adverse device effect

Severity	Definition
Mild	Awareness of effect but easily tolerated
Moderate	Discomfort enough to cause some interference with usual activity
Severe	Inability to carry out usual activity

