8.6. Safety Analysis

Information on adverse device effects (ADEs) that are considered to be definitely related to the DSS will be collected. These ADEs will be tabulated for the DSS arm only and stratified by severity. Data will be presented as the number of patients with at least one ADE, and as the number of ADEs reported.

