12.5.3. Binary outcomes

Table 27: Effect of DSS on proportion of patients receiving LLT combination therapy

Patients receiving LLT combination therapy	Trial arm		Adjusted Risk Ratio*	95% confidence interval
	DSS	Control		
N (missing)			x.xx	x.xx to x.xx
n (%)				

*adjusted for country, site type (secondary/ tertiary care/mix of both) and study site

Table 28: Effect of DSS on proportion of patients receiving escalated LLT monotherapy

Patients receiving escalated LLT monotherapy	Trial arm		Adjusted Risk Ratio*	95% confidence interval
	DSS	Control		
N (missing)			x.xx	x.xx to x.xx
n (%)				

*adjusted for country, site type (secondary/ tertiary care/mix of both) and study site

Table 29: Effect of DSS on proportion of patients receiving escalated LLT combination therapy

Patients receiving escalated LLT combination therapy	Trial arm		Adjusted Risk Ratio*	95% confidence interval
	DSS	Control		
N (missing)			x.xx	x.xx to x.xx
n (%)				

*adjusted for country, site type (secondary/ tertiary care/mix of both) and study site

Table 30: Effect of DSS on reaching target LDL-C levels

Patients with target LDL-C levels, <1.4 mmol/L (<55 mg/dL) by week 16	Trial arm		Adjusted Risk Ratio*	95% confidence interval
	DSS	Control		
N (missing)			x.xx	x.xx to x.xx
n (%)				

*adjusted for country, site type (secondary/ tertiary care/mix of both) and study site

12.6.Safety Analysis

Table 31: Adverse Device Effects by trial arm

	DSS arm only	
	No. of patients (%)	No. of events
ADE		
SADE		
USADE		
ASADE		

Table 32: Severity of Adverse Device Effects by trial arm

	DSS arm only	
	No. of patients (%)	No. of events
ADE		
Mild		
Moderate		
Severe		

Table 33: Relatedness of Adverse Device Effects by trial arm

	DSS arm only	
	No. of patients (%)	No. of events
ADE		
Related		
Serious and Related		
Serious, Related and Unanticipated		

Table 34: Type of Adverse Device Effects by trial arm

	DSS arm only	
	No. of patients (%)	No. of events
System Organ Class		
Preferred Term		
.....		

12.7.Subgroup Analysis

Forest plots will be presented for subgroup of interested listed in Section 8.8.

12.8.Exploratory Analysis

Table 35: Exploratory endpoints by Week 16 (all patients)

Endpoint	Trial arm		
	DSS	Control	Overall
Patients achieving target LDL-C level <1.8 mmol/L (<70 mg/dL) by Week 16			
N (missing)			
n (%)			
Patients on combination therapies with three oral LLT or 1 injectable therapy plus one or more oral LLT			
N (missing)			
n (%)			
Mortality before Week 16			

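### SAP 8.6 limits adverse device effects to those graded definitely related, in conflict with SAP 5.4, so Possible and Probable effects, including serious ones, would go unreported

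*SAP*

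**What the plan says.** SAP 5.4 lists the safety variables to be reported for the DSS arm: ADEs, SADEs and, among the SADEs, unanticipated (USADE) and anticipated (ASADE) effects. It sets no causality threshold. The definition is "Adverse Device Effects (ADE): Any untoward and unintended response to a medical device", and it extends to events caused by poor instructions or deployment of the device. On grading it says: "The assignment of causality and severity for adverse device effects should be made by the investigator responsible for the care of the patient". Table 3 supplies five causality grades: Unrelated, Unlikely, Possible, Probable and Definite. Probable is defined as "There is evidence to suggest a causal relationship and the influence of other factors is unlikely". Definite is defined as "There is clear evidence to suggest a causal relationship and other possible contributing factors can be ruled out".

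SAP 8.6 says: "Information on adverse device effects (ADEs) that are considered to be definitely related to the DSS will be collected". Its next sentence makes those same ADEs the ones to be tabulated by severity in the DSS arm. SAP 12.6 lays out Tables 31 to 34, including Table 33, "Relatedness of Adverse Device Effects by trial arm". SAP 8.7 puts adverse device events into the closed TEC reports.

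**The concern.** Sections 5.4 and 8.6 describe two different data sets. Under 5.4, an untoward response to the device is reportable and is then graded. Under 8.6, it enters the data only if it has already reached the top grade. An effect graded Probable, even a serious one, would not be counted as an ADE, SADE or USADE.

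The top grade is demanding in this trial. The DSS acts through a prescriber: SAP 4.2 says "Implementing the patient-specific recommendation remains at the" clinician's discretion. The patients have had a recent ACS event and may be taking several other medicines (Table 15). When harm arises through a treatment choice, another contributing factor will often be hard to rule out, so a real device effect may be graded no higher than Probable.

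What is at stake is the completeness of the device-safety tables and of what the TEC sees. A limit on collection cannot be repaired at analysis. The efficacy analyses are not affected.

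**Working it through.** **1. The sections side by side**

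| Item | SAP 5.4 | SAP 8.6 |
|---|---|---|
| Which ADEs | any untoward, unintended response to the device | those considered definitely related |
| Causality grades that can appear | five | one |
| A serious effect graded Probable | an SADE, and a USADE if unanticipated | not collected, not tabulated |

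Three of the five grades (Possible, Probable, Definite) assert at least some evidence of a causal link. Section 8.6 keeps one of those three.

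**2. Effect on Table 33**

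Its rows are Related; Serious and Related; and Serious, Related and Unanticipated. Table 31 has ADE, SADE, USADE and ASADE. If every ADE in the data is already definitely related, then:

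- Related = the ADE count
- Serious and Related = the SADE count
- Serious, Related and Unanticipated = the USADE count

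Section 5.4 adds that no ASADEs have been identified, so the SADE and USADE counts should also agree. Table 33 adds information only if ADEs of differing relatedness are recorded, as 5.4 implies.

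**3. Can the loss be sized?**

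Section 8.6 gives no figure to reproduce. The DSS-arm denominator comes from SAP 4.5: 24 clusters × 33 patients = 792. Two further inputs are needed, and the documents give neither:

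- r, the proportion of DSS patients with an ADE graded Possible or higher
- s, the share of those patients with an ADE graded Definite

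The values below are assumptions, with patients treated as independent. The chance of an empty table is (1 − r·s)^792 under 8.6, and (1 − r)^792 if Possible, Probable and Definite are all collected.

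| r | s | Expected patients, all three grades (792·r) | Expected, Definite only (792·r·s) | P(empty), 8.6 | P(empty), all three grades |
|---|---|---|---|---|---|
| 0.1% | 10% | 0.79 | 0.08 | 0.92 | 0.45 |
| 0.5% | 10% | 3.96 | 0.40 | 0.67 | 0.02 |
| 1% | 10% | 7.92 | 0.79 | 0.45 | <0.001 |
| 1% | 50% | 7.92 | 3.96 | 0.02 | <0.001 |
| 5% | 10% | 39.6 | 3.96 | 0.02 | <0.001 |

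The restriction raises the chance of an empty table in every row, but the chance under 8.6 runs from 0.92 down to 0.02. At r = 0.01% the table would be empty with probability 0.92 even if all three grades were collected. The direction of the bias is certain; its size is not.

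**The case against.** The best case for the plan has four parts.

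- **Section 5.4 may govern in practice.** It commits to all ADEs, and the protocol text available here begins inside section 9 and has no safety-reporting section, so actual collection cannot be checked. This stands as a limit on what can be said about collection. It does not rescue the tables, because 8.6 also tabulates only the definitely related ADEs.
- **There is other safety information.** A reader might infer that these tables are the trial's only device-safety output. They are not. SAP 7.2 captures device deficiencies at DSS sites with no causality filter. Mortality is tabulated by arm (8.4), mortality and cardiovascular events appear by arm in Table 35, and Table 21 counts non-completion for death or adverse event. For a tool that works through prescribing, randomised counts by arm may say more about harm than investigator attribution does. All of that stands. But deficiencies are malfunctions, user errors and software inadequacy, with no row in Tables 31 to 34, and the event counts carry no attribution to the device. Neither restores the missing graded ADEs.
- **Definite is attainable.** The ADE definition covers faulty instructions and deployment, where firm attribution is feasible. This stands, and it counts against any claim that the tables must be empty.
- **Table 33 was never laid out by grade.** True, and Definite events would still fill it. The weakness is duplication of Table 31, not an absence of content.

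**Conclusion.** Sections 5.4 and 8.6 conflict. Followed as written, 8.6 omits Possible and Probable ADEs, including serious ones, from Tables 31 to 34 and from the adverse device events given to the TEC. Device-related effects are therefore under-reported, the tables may be sparse or empty, and Table 33 largely repeats Table 31. This rests on reading 8.6 literally and on no other section restoring the lower grades; none in the text available does.

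Two stronger readings should be resisted. A reader might infer that the ADE tables will be empty however the device performs. That needs an ADE rate and a Definite share, and the documents give neither. A reader might also use the upper confidence limit for a zero count in 792 patients as the size of the problem. Such a limit would apply to Definite effects only and would not measure how many lower-grade effects were lost.

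**What to change.** Reconcile 8.6 with 5.4:

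- Reword 8.6 so that all ADEs, SADEs and USADEs graded Possible, Probable or Definite in Table 3 are collected and tabulated for the DSS arm.
- Show the counts in Table 33 by Table 3 causality grade, for all ADEs and for serious ones, in place of the single Related category.
- Put the same table in the closed TEC reports under 8.7.
- Check the protocol's safety-reporting section. If it already collects all grades, correct 8.6 to match it.

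The cost is SAP and eCRF-guidance wording, a few table rows, and a few more reports from DSS sites, using a grading step that 5.4 already asks of investigators. The change should be made before more data accrue, because effects that were never recorded cannot be recovered at analysis.

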8.7. Interim Analysis

The Trial Executive Committee will review safety data at the timepoints of their choosing. No statistical hypothesis testing will be completed for the TEC.

The statistician will analyse the interim data at the request of the TEC meeting and act as a data manager, in raising and resolving data queries with participating sites, via the Trial Manager. Closed TEC reports will include recruitment, randomisation balance and stratification effectiveness, baseline characteristics, withdrawals, concomitant medications and adverse device events. Open TEC reports will be provided without outcome or arm information. Interim analyses do not involve formal statistical hypothesis testing; as a result, no adjustment for interim analyses has been made.

Imperial Clinical Trials Unit	ZODIAC STATISTICAL ANALYSIS PLAN – MAIN ANALYSIS	V1 17 th Jan 2024
-------------------------------	--	------------------------------

In addition, as described in Section 5.2, we will complete periodic blinded validation checks on the algorithm used to assign the trial's primary outcome.

8.8. Subgroup Analysis (of Primary Outcome)

Subgroup analysis will follow the same analysis of the primary outcome with the addition of an interaction term between the treatment and the subgroup analysis variables. These will be summarised by forest plots.

The variables investigated in the subgroup analyses are (at patient level):

- gender (men vs women)
- age (below vs above or equal to median age)
- diabetes (yes vs no)
- LLT naïve (yes vs no)
- patients experiencing one or more CV event in the 2 years prior to admission

Below is an example model for an interaction between intervention and gender added.

$$\log(\pi_{ij}) = \beta_0 + \beta_1 ACSDSS_{ij} + \beta_2 COUNTRY1_{ij} + \beta_3 COUNTRY2_{ij} + \beta_4 Site\ type_{ij} + \beta_5 Site\ type_{ij} + \beta_6 Gender_{ij} + \beta_7 ACSDSS_{ij} * Gender + U_j$$

Where:

- π_{ij} : probability of combination therapy for the i^{th} patient in j^{th} site
- $ACSDSS_{ij}$: dummy variable for intervention ($ACSDSS_{ij} = 0$ or 1) for patient i in j^{th} site
- $COUNTRY1_{ij}, COUNTRY2_{ij}$: dummy variable for COUNTRY ($COUNTRY_{ij} = 0$ or 1) for patient i in j^{th} site
- $Site\ type1_{ij}, Site\ type2_{ij}$: dummy variable for Site Type ($Site\ type_{ij} = 0$ or 1) for patient i in j^{th} site type
- U_j : random effect for site $j \sim N(0, \sigma_u^2)$
- $Gender_{ij}$: dummy variable for gender of patient i in j^{th} site

Subgroup analyses at cluster level by site type is not planned as the number of sites is anticipated to be small for some strata.

Imperial Clinical Trials Unit	ZODIAC STATISTICAL ANALYSIS PLAN – MAIN ANALYSIS	V1 17 th Jan 2024
-------------------------------	--	------------------------------

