4.5. Sample Size

It is estimated that in the SoC arm, we expect 7% of patients to be on combined therapy at 24 weeks. This estimate is based on published data (Koskinas et al³) using the ELIPS study cohort which included exclusively ACS patients. A slightly lower proportion of patients (5%) may be expected to be on combination therapy at 16 weeks.

To detect a meaningful difference in proportions from the SoC group of 0.05 to 0.15 in the DSS with 90% power, we require 744 patients in 24 clusters within each arm.

This calculation assumes a two-sided statistical test at the 5% significance level, ICC of 0.1 and clusters of a similar size (31 for each site).

Justification for ICC of 0.1: Based on the article by Campbell et al.⁴, it would be reasonable for a guideline implementation study within primary care to assume an ICC of the order of 0.1 for process variables and an ICC of less than 0.05 for the outcome variable. This is also in line with empirical estimates obtained from an online database with ICC reported for cluster studies that aimed to change practice.⁵ In the database we examined the hypertension guideline interventions, these varied from 0.048 to 0.064. In addition, we have to consider clustering within country; to be conservative we have assumed an ICC of 0.1.

Based on our experience working in this setting we do not expect any loss of clusters. However, drop out may occur within clusters. As data are extracted from routinely collected electronic healthcare records, we expect missing data to be low as it will only be patients who actively request data collection to stop that will have missing outcome data. Considering a conservative approach⁶ and assuming a loss to follow-up rate of 5%, we need a minimum total sample size of 1568. Considering adjusted numbers per cluster we aim to recruit 792 over 24 clusters per arm (a total sample size of 1584).

Imperial Clinical Trials Unit	ZODIAC STATISTICAL ANALYSIS PLAN – MAIN ANALYSIS	V1 17 th Jan 2024
----------------------------------	--	------------------------------

All calculations were done using PASS 2022 software⁷ and applying a method of “Tests for Two Proportions in a Cluster-Randomised Design”.

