5.2. Primary Efficacy Variable

Proportion of patients with intensification of LLT relative to baseline, regardless of adherence to the DSS, within 16 weeks of index ACS event.

Intensification includes:

- escalation of monotherapy OR
- initiation of combination therapy OR
- escalation of combination therapy

Only commercially available licensed LLT will be considered.

Patients will be considered LLT-naïve on admission if no LLT medications (statins, ezetimibe, bempedoic acid, bile acid sequestrants, evolocumab, alirocumab and inclisiran) are listed on the LLT 'prior to admission' form which captures LLT therapy in the month prior to admission. Patients who are admitted on medicines such as fish oils, nicotinic acid derivatives and fibrates will be considered to be a subgroup of LLT-naïve patients since these agents do not have a clinically significant effect on LDL levels.

Patients who are LLT-naïve on admission will be expected to start on statin monotherapy prior to discharge or an alternative monotherapy prior to discharge, and rarely post-discharge i.e. during follow up. For patients initiated on monotherapy as their first LLT, intensification of therapy in these patients can only occur after starting monotherapy. Therefore, the primary outcome will be met in these patients if they subsequently receive escalation of their monotherapy or start combination therapy during follow up. It is also possible that some LLT-naïve patients may be started on combination therapy at discharge. In this case the primary outcome will be met at discharge.

For patients who are already prescribed LLT prior to admission, they will meet the primary outcome if intensification occurs between admission and discharge or after discharge.

Table 2: Primary outcome definition

Baseline therapy patients recruited with	Meets primary outcome at 16 weeks if the patients is now on
<2 LLT drugs (i.e. 0 to 1)	Combination therapy (2 or more drugs) OR
	Escalated monotherapy (one drug increase in dose, or switch to more potent single drug)

Imperial Clinical Trials Unit	ZODIAC STATISTICAL ANALYSIS PLAN – MAIN ANALYSIS	V1 17 th Jan 2024
-------------------------------	--	------------------------------

>=2 LLT drugs	Escalated combination therapy (e.g. 3 drugs, increase in the potency of one of the drugs if the total number of drugs remains unchanged)
---------------	--

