8.4. Primary Efficacy Analysis

The primary outcome measure, the proportion of patients treated with combination therapy, or who receive escalated monotherapy, or escalated combination therapy, within 16 weeks of the index ACS (regardless of adherence at 16 weeks) will be modelled using a generalised linear mixed model. This model will use a binomial distribution, log link function and with fixed effect for country and site type (secondary/tertiary care/mixed) and a random effect for study site (as a random intercept). If there is a convergence problem with the log-binomial model, Poisson regression with robust standard errors (modified Poisson regression) will be used. The intervention effect will be reported as a Risk Ratio with a 95% confidence interval. For primary analysis hypotheses will be tested as two-sided with a significance level of 0.05.

$$\log(\pi_{ij}) = \beta_0 + \beta_1 ACSDSS_{ij} + \beta_2 COUNTRY1_{ij} + \beta_3 COUNTRY2_{ij} + \beta_4 Site\ type_{ij} + \beta_5 Site\ type_{ij} + U_j$$

Where:

Imperial Clinical Trials Unit	ZODIAC STATISTICAL ANALYSIS PLAN – MAIN ANALYSIS	V1 17 th Jan 2024
-------------------------------	--	------------------------------

- π_{ij} : probability of combination therapy for the i^{th} patient in j^{th} site
- $ACSDSS_{ij}$: dummy variable for intervention ($ACSDSS_{ij} = 0$ or 1) for patient i in j^{th} site
- $COUNTRY1_{ij}, COUNTRY2_{ij}$: dummy variable for COUNTRY ($COUNTRY_{ij} = 0$ or 1) for patient i in j^{th} site
- $Site\ type1_{ij}, Site\ type2_{ij}$: dummy variable for Site Type ($Site\ type_{ij} = 0$ or 1) for patient i in j^{th} site type
- U_j : random effect for site $j \sim N(0, \sigma_u^2)$

This model will use the modified intention-to-treat population and will include all eligible and randomised patients through use of multi-level multiple imputation. If any participants die within 16 weeks they will be excluded from this primary analysis and any similar secondary outcome analysis but will be included in the time to event outcomes (until censored). We will tabulate mortality by intervention arm.

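### The subgroup interaction model in SAP 8.8 leaves site-to-site variation in the subgroup gap out of its standard error, and the SAP's text and example code disagree on how that error is computed

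*SAP*

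**What the plan says.** SAP 8.8 plans subgroup analyses of the primary outcome by gender, age, diabetes, LLT-naïve status and recent CV event. Each uses the primary analysis "with the addition of an interaction term between the treatment and the subgroup analysis variables". The worked formula for gender adds a main effect and an arm-by-gender product, and keeps a single normal site effect, U_j. That follows SAP 8.4, whose log-binomial model has fixed effects for country and site type "and a random effect for study site (as a random intercept"). If that model fails to converge, 8.4 switches to Poisson regression with robust standard errors, without saying whether they are clustered by site.

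The example code for the primary outcome (Appendix D, 14.1) is different. It is a log-link binomial `glm` with `vce(cluster site)` and no random effect, although its comment calls it a mixed model. Appendix D has no code for the subgroup analyses.

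Results go into forest plots (8.8, 12.7, Appendix C). No interaction p-value or decision rule is stated there. SAP 8.1 sets a general 0.05 level with 95% confidence intervals.

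**The concern.** All patients at a site share one arm, so the arm-by-subgroup term compares within-site subgroup gaps at 24 DSS sites with those at 24 SoC sites. A site intercept shifts both subgroups equally and cancels out of the gap. The written model therefore treats the true gap as identical at every site within an arm. If it is not, part of the ordinary variation between sites is read as interaction.

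The plan itself gives a reason to expect some variation for LLT-naïve status. Under SAP 5.2, naïve patients started on monotherapy can score only after that start. For pre-treated patients, "they will meet the primary outcome if intensification occurs between admission and discharge or after discharge". A site's inpatient and follow-up prescribing habits can therefore act differently on the two groups.

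At stake is secondary inference. A forest plot could suggest that the DSS works better in one subgroup when only site practice differs.

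**Working it through.** **Inputs (SAP 4.5).** Event proportions of 5% (SoC) and 15% (DSS), 90% power, two-sided 5% level, 24 sites and 744 patients per arm. The clustering inputs are "ICC of 0.1 and clusters of a similar size (31 for each site").

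**The plan's own figure.** With the unpooled normal formula, n = (1.960 + 1.282)² × (0.05×0.95 + 0.15×0.85) / 0.10² = 183.9 per arm. The design effect is 1 + 30×0.1 = 4.0, giving 735.5, or 24 sites of 31 = 744. Power at 744 is 90.3%. With 5% loss, 744/0.95 rounds up to 784 per arm, 1568 in total; 48×33 = 1584. The sample size reproduces. It concerns the arm effect, and the documents state no error rate for interactions.

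**Formula for the interaction test.** Let ρ be the between-site correlation of the two subgroups' site effects (assumed; not in the documents). On a scale with total variance 1:

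- Within-site variance of a site's gap: w = (1 − ICC)(1/n₁ + 1/n₀).
- Between-site variance of the gap: τ² = 2(1 − ρ)·ICC.
- The written model uses w where w + τ² is needed, so the size is 2{1 − Φ(1.96/√(1 + τ²/w))}.

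Example: ICC 0.1, 31 patients split 50:50, ρ = 0.5. Then w = 0.9 × 2/15.5 = 0.116, τ² = 0.1, and the variance ratio is 1.86. The size is 2{1 − Φ(1.437)} = 15.1%.

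| ICC | ρ | Ratio (50:50) | Size, 50:50 | Size, 25:75 | Size, 10:90 |
|---|---|---|---|---|---|
| 0.1 | 1 | 1.00 | 5.0% | 5.0% | 5.0% |
| 0.1 | 0.8 | 1.34 | 9.1% | 8.1% | 6.4% |
| 0.1 | 0.5 | 1.86 | 15.1% | 12.7% | 8.7% |
| 0.05 | 0.8 | 1.16 | 6.9% | 6.4% | 5.7% |
| 0.05 | 0.5 | 1.41 | 9.9% | 8.6% | 6.7% |

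**Simulation of the written model.** 48 sites, no true interaction, country and site type omitted from data and model, Wald test at 1.96.

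- Log link, 31 per site, event rates 10–25%, 600 runs per cell (Monte Carlo error 0.9–1.6 points):
  - ICC 0.1, 50:50: about 6% at ρ = 1, 13.7–14.2% at 0.8, 19.3–20.3% at 0.5.
  - ICC 0.1, 25:75: 11.3–12.8% at 0.8, 16.0–17.7% at 0.5.
  - ICC 0.05: 6.7–9.3% at 0.8, 9.7–12.5% at 0.5.
- Log link, 33 per site, ICC 0.1, a 20% subgroup, 500 runs: 9.4% at 0.8 and 15.8% at 0.5.
- Log link, 250 runs per cell (error about 1.5–2.5 points), ICC 0.1: 9–13% at 0.8 and 10–21% at 0.5.
- Logistic stand-in, 31 per site, ICC 0.1, 1000 runs: 4–6% at ρ = 1, 8–10% at 0.8, 12–15% at 0.5. With the rarer subgroup, sizes were slightly lower at the lower event rates.

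**Site-clustered variance on the same kind of data.** With a t reference on 46 df: 4.3–6.2% in one set of runs, and 2–9% per cell (average about 6%) in a smaller set. With a normal reference: 4.7–8.5%.

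**What ρ implies.** At a 10% event rate and ICC 0.1, the site SD on the log scale is √ln(1 + 0.1×0.9/0.1) = 0.80, and the gap SD is 0.80 × √(2(1 − ρ)). At ρ = 0.8 this is 0.51, so 95% of sites have a subgroup risk ratio within 0.37 to 2.7 times the typical one. At ρ = 0.5 it is 0.80, and the span is 0.21 to 4.8.

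**The case against.** A reader might infer that, under the plan's own ICC, these tests reject a true null 11–21% of the time. The documents do not support that. The ICC fixes the overall site variance, not the variance of the gap; at the same ICC of 0.1 the size is about 5% when the gap is constant. The 0.1 is itself an upper choice: the SAP found 0.048 to 0.064 for comparable interventions and, with clustering by country in mind, wrote "to be conservative we have assumed an ICC of 0.1". The 8.8 model adjusts for country, so the residual ICC may be lower. Correlation 0.5 also implies large differences between sites, which nothing in the documents supports for gender, age or diabetes. For LLT-naïve status, the scoring rule common to all sites is absorbed by the main effect; how much sites vary around it is conjecture.

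Nor do 8.8 and 12.7 set up formal tests with a decision rule. And 8.8 follows the primary analysis, whose example code already clusters by site.

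All of this limits the size of the problem. It does not remove it. Intervals that are too narrow mislead in a forest plot with or without a printed p-value. The protection in 14.1 contradicts the model written in 8.4 and 8.8, and the robust errors in 8.4 apply only if the model fails to converge. As it stands, the validity of the interaction depends on which part of the SAP the programmer follows.

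**Conclusion.** The point holds in conditional form. The omission from the 8.8 standard error is certain; its effect is not known. For a nominal 5% test the range is about 5% with a constant gap. At ICC 0.1 it is roughly 8–14% at correlation 0.8 and 10–21% at 0.5, with rarer subgroups (and, more weakly, lower event rates) towards or below the lower ends. At ICC 0.05 it is about 6–12% over the same correlations. These figures rest on an assumed correlation and subgroup prevalence, and on simulations without country or site type. They tested the interaction only; the subgroup-specific intervals share the omission, but its size there was not measured.

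The conflict between 8.4/8.8 and 14.1 needs no assumption. The primary comparison's sample size is not in question. This is a worthwhile, inexpensive correction to secondary inference.

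**What to change.** - In 8.8, state that the arm-by-subgroup interaction, the subgroup-specific risk ratios and their confidence intervals all come from one log-link model with variance clustered by site. Use a t reference on site-level degrees of freedom: 48 − 2 = 46, or 42 after two terms each for country and site type.
- Reconcile 8.4 and 8.8 with Appendix D: say which model is used, say whether the robust errors in the Poisson fallback are clustered by site, and add example code for a subgroup model.
- A random subgroup slope by site can be a sensitivity analysis where it converges. It should not lead: it has not been tried here, and 33 patients at event rates of 5–15% give only about 2 to 5 events per site (33×0.05 = 1.7; 33×0.15 = 5.0) before splitting by subgroup.

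The cost is SAP wording and a few lines of code of a kind the SAP already contains, with no new data. Interaction intervals become slightly wider, and a small excess over 5% may remain with 24 sites per arm.
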